4.4.8 Secondary Endpoint 8: Patient Radiation Exposure

Endpoint: Dose Area product (DA, mGy*cm²) and Air Kerma (AK, mGy) as recorded on the CRF 6 Procedure Data Form CRF.

Subjects to Include: Analysis Cohort

Statistical Analysis: The mean, standard deviation, median, interquartile range, and range along with a 2-sided 95% confidence interval for the mean will be calculated.

4.4.9 Secondary Endpoint 9 Contrast Fluid Volume

Endpoint: Total volume of contrast used during the procedure as recorded on the CRF 6 Procedure Data Form CRF.

Subjects to Include: Analysis Cohort

Statistical Analysis: The mean, standard deviation, median, interquartile range, and range along with a 2-sided 95% confidence interval for the mean will be calculated.

4.4.10 Secondary Endpoint 10: Adverse Events

Endpoint: All adverse events (AEs) from the start of the CorPath GRX procedure until the end of the study as recorded on CRF 11 Adverse Event / Serious Adverse Event CRF.

Subjects to Include: Analysis Cohort

Statistical Analysis: The count and percentage of subjects experiencing AEs will be summarized by Adverse Event Term and include breakdowns by seriousness and relatedness to device and procedure.

4.4.11 Secondary Endpoint 11: Thromboembolic Events

Endpoint: Defined as thromboembolic events occurring up to 180-days following the robotic-assisted procedure.

Subjects to Include: Analysis Cohort

Statistical Analysis: The count and proportion of subjects with a thromboembolic event through 180-days following the robotic-assisted procedure will be calculated along with a 2-sided Clopper Pearson Exact 95% confidence interval.

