#### **4.7 Subject Withdrawal and Replacement**

Subjects enrolled in the study can discontinue their participation at any time for any reason without prejudice or reduction in the quality of their medical care. The investigator can terminate a subject's participation in the study to protect the subject's health, if the subject fails to follow instructions or if the subject is unable to keep appointments. The Investigator must then document this notification of withdrawal from the study in the appropriate CRF and notify the sponsor. No replacements will be allowed. Up to 120 subjects will be enrolled in order to achieve data on 108 subjects. All data will be included in summaries.

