4.1 Definition of Analysis Populations

Analysis Cohort: Any subject with an attempted endovascular procedure (a non-missing robotic microcatheter insertion time).

Per-Protocol Cohort: Any subject in the analysis cohort who did not have a major protocol deviation.

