4.5 Additional Summaries

Some additional summaries will be prepared:

- Descriptive statistics of the population
 - Demographics and patient baseline characteristics

- Aneurysm characteristics
- Procedures performed
- Malfunctions
- Protocol deviations

5 Data Conventions and Missing Data

It is assumed that because the primary and most secondary analyses are evaluated within twenty-four (24) hours of CorPath GRX procedure or prior to hospital discharge, whichever occurs first, there will be no missing data. For the 90-day and 180-day secondary endpoints (modified Rankin Scale, thromboembolic events, and aneurysm occlusion), all practical monitoring and follow-up steps will be taken to ensure complete and accurate data collection. Additionally, all data collected on safety or adverse events will be reported to the extent they are available.

6 Appendix 1: Adverse Event Classification and Definitions

An Adverse Event (AE) is any untoward medical occurrence, unintended disease or injury, or untoward clinical signs (including abnormal laboratory findings) in subjects, users or other persons, whether or not related to the investigational medical device.

A Serious Adverse Event (SAE), as per the European Standard ISO 14155 (E), is an AE that:

- Led to death
- Led to a serious deterioration in the health of a patient that:
- Resulted in a life-threatening illness or injury
- Resulted in a permanent impairment of a body function or body structure
- Required in-patient hospitalization or prolonged hospitalization
- Resulted in medical or surgical intervention to prevent permanent impairment to a body function or body structure
- Led to fetal distress, fetal death or a congenital abnormality or birth defect.

In the current study indication, a SAE can be defined as an adverse event where the outcome is one of the following:

- Incidence of death 24 hours post procedure
- Target aneurysm rupture
- Vessel perforation
- Vessel dissection
- Thromboembolic complication
- Failure to navigate to target
- Device failure to respond to input, or other intra-operative device failure

Adverse Event Assessments

Relatedness:

- Procedure-related: Event has a strong temporal relationship to the study procedure. This includes AEs attributable to any device(s) used at procedure, such as access devices, delivery microcatheters, embolic coils, non-ionic contrast, guidewires, or any other adjunctive, approved/cleared device for treatment of intracranial aneurysms.

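### The 180-day thromboembolic rate is planned as a simple proportion, with no rule for subjects observed for less than 180 days

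*SAP*

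**What the plan says.** SAP 4.4.11 defines the endpoint as thromboembolic events up to 180 days. The analysis is: "The count and proportion of subjects with a thromboembolic event through 180-days following the robotic-assisted procedure will be calculated", with a two-sided Clopper-Pearson 95% interval. The population line reads "Subjects to Include: Analysis Cohort", and SAP 4.1 defines that cohort as "Analysis Cohort: Any subject with an attempted endovascular procedure (a non-missing robotic microcatheter insertion time"). The cohort has no minimum follow-up, and the endpoint has no censoring rule.

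On missing data, SAP section 5 has two separate statements. The first covers analyses done by 24 hours or discharge: because "the primary and most secondary analyses are evaluated within twenty-four (24) hours of CorPath GRX procedure" or before discharge, the SAP expects that "there will be no missing data". The second covers the late endpoints: "For the 90-day and 180-day secondary endpoints (modified Rankin Scale, thromboembolic events, and aneurysm occlusion), all practical monitoring and follow-up steps will be taken". It describes effort in data collection and gives no analysis rule. Protocol 6.9 has the same structure, but expects minimal missing data for the early analyses where the SAP expects none.

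Protocol 4.7 states that "Subjects enrolled in the study can discontinue their participation at any time for any reason", and allows no replacements. Protocol 4.8.10 makes the 90-day contact a telephone call and gives the 180-day visit a window of ±30 days. The opening of Protocol section 6 includes treated subjects in primary and secondary endpoints to the extent that their data exist.

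**The concern.** A proportion with a fixed denominator estimates a 180-day risk only if every subject in the denominator was observed for 180 days, had the event, or died first. Some subjects here will meet none of these conditions: those who withdraw, those who cannot be reached, and those whose final visit falls as early as day 180 − 30 = 150, which is within the protocol. A subject last seen at day 20 without an event contributes 20 days of information but is entered as 180 days without an event.

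At stake are the accuracy of one late safety rate and its reproducibility. Because the documents do not settle the denominator, two analysts could report different rates from the same data, and the choice could be made after the results are known. The exact interval also treats partly observed subjects as fully observed.

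**Working it through.** **The plan's own figures.** The plan gives no expected rate, precision or loss rate for this endpoint, so there is nothing to reproduce for it directly. The sample size that fixes the denominator does reproduce. For 80% against 90% at one-sided 0.025, the normal approximation gives 107.4, so 108 subjects, and the exact test (success at 95 or more of 108) has 81.0% power. The enrolment ceiling agrees with a 10% allowance, 108 / 0.90 = 120, but the documents do not say that this allowance is for loss before day 180.

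**Inputs, all assumptions.**
- True 180-day risk R = 6%. For orientation only, SAP Table 2 lists embolism rates for unruptured aneurysms of 2.82% (pooled) and 6.2% (20/325, a coil-alone series). Neither is given as a 180-day rate.
- Share of that risk arising late, s = one half, so late risk = 3%.
- Loss fraction L = 10%, unrelated to risk.
- m = fraction of the lost subjects' late events that is missed: 1.0 if loss comes before all of them, about 0.5 if loss is spread evenly over follow-up.

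**Reading 1: full Analysis Cohort, lost subjects counted as event-free.**

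Expected reported rate = R − L × (s × R) × m

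| Loss | Late share | m = 0.5 | m = 1.0 |
|---|---|---|---|
| 10% | half | 6 − 0.10 × 3 × 0.5 = 5.85% | 6 − 0.10 × 3 × 1 = 5.70% |
| 10% | all | 6 − 0.10 × 6 × 0.5 = 5.70% | 6 − 0.10 × 6 × 1 = 5.40% |
| 20% | half | 6 − 0.20 × 3 × 0.5 = 5.70% | 6 − 0.20 × 3 × 1 = 5.40% |
| 20% | all | 6 − 0.20 × 6 × 0.5 = 5.40% | 6 − 0.20 × 6 × 1 = 4.80% |

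The last cell in each pair of rows is the extreme in which no event of a lost subject is seen before loss. If loss is unrelated to risk, the relative shortfall cannot exceed the fraction lost. If all events precede loss, there is no shortfall. If subjects leave because of an event that is never reported, the shortfall can exceed this bound.

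**Reading 2: denominator cut to subjects with full follow-up, early events of lost subjects kept.**

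With 10% loss and half the risk late, divide the events seen by the 90% retained: 5.70 / 0.90 = 6.33% and 5.85 / 0.90 = 6.50%, against a true 6%. Keeping lost subjects with events in the denominator too changes this little: per 100 subjects, 5.70 / 90.30 = 6.31% and 5.85 / 90.45 = 6.47%. If the early events of lost subjects are dropped as well, this upward bias goes, but observed safety events are discarded.

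**Scale against the interval.** Suppose 120 subjects are treated, 12 are lost and 6 events are recorded:
- On 120: 5.0%, exact interval 1.9% to 10.6% (width 8.7 points).
- On 108: 5.6%, exact interval 2.1% to 11.7% (width 9.6 points).

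The choice of denominator moves the estimate by 0.6 points. The Reading 1 bias at 10% loss with half the risk late is 6.00 − 5.85 = 0.15 to 6.00 − 5.70 = 0.30 points. Both are small beside an interval about 9 points wide.

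**The case against.** The strongest case against acting is that nothing depends on this rate. It has no hypothesis and no performance goal; only the two primary endpoints do. All adverse events to study end are summarised separately in SAP 4.4.10, and the bias is well inside the sampling error. Thromboembolic events with neurological decline are part of the primary safety endpoint because they are expected around the procedure. The one 180-day trial in Protocol Table 5 shows ischemic stroke of 2.8% (3/107) in its perioperative row and no figure in the delayed rows, although the device differs and the table may not have been read cleanly. If most events are early, the shortfall is close to nil. All of this stands, and it limits how much weight the point can bear.

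A second argument is that Protocol section 6 already permits an available-data denominator. It does, but it does not define availability for an event endpoint. As Reading 2 shows, that route either pushes the rate up or discards early events.

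Four stronger readings are tempting, and the documents do not support them:
- That the SAP assumes complete data for this endpoint. The words "whichever occurs first, there will be no missing data" belong to the analyses done by 24 hours or discharge. The next sentence treats the late endpoints separately and names thromboembolic events.
- That the bias must favour the device. This holds only if the full cohort is the denominator, and no text says that lost subjects count as event-free.
- That a subject who dies early without an event is mis-scored. Such a subject cannot have the event later, so counting no event by day 180 is correct for cumulative incidence.
- That this is the trial's main late safety result. Neither document ranks it so.

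**Conclusion.** The gap is real and minor. SAP 4.4.11 specifies a simple proportion on a cohort with no follow-up requirement, and no section says how partial follow-up enters the numerator or the denominator. The literal reading biases the rate low, and the likeliest alternative biases it high. On the stated assumptions (6% true risk, half late, 10% loss unrelated to risk), the low-side figure is 5.7% to 5.85%, with 5.4% as the extreme, and the high-side figure is about 6.3% to 6.5%. The event rate, late share and loss fraction are all assumed, and loss linked to unreported events would make the low-side bias larger. The effectiveness and safety conclusions are untouched. The point is worth making because the remedy costs almost nothing and removes a choice that could otherwise be made after seeing the data.

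**What to change.** In SAP 4.4.11:
1. Estimate the 180-day rate by cumulative incidence of the first thromboembolic event, with a 95% interval. Censor event-free subjects at last contact or day 180, whichever is earlier, and treat death without a thromboembolic event as a competing event.
2. Report the number of subjects with complete 180-day follow-up.
3. Keep the crude count and proportion on the Analysis Cohort, with its Clopper-Pearson interval, as a supporting line. Use that interval as the reported one if there are no events.

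No new data are needed. Protocol section 5 already records adverse event onset dates, and Protocol 7.7 requires visit dates and the study exit date in the medical record. The cost is a few lines of SAP text and slightly more analysis work. The reported rate will usually be slightly higher and its interval slightly wider than the crude one, and with few events the interval is approximate, which is a reason to keep the exact interval beside it.

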4.4.12 Secondary Endpoint 12: Devices Used Robotically

Endpoints: All devices used will be recorded as successful or unsuccessful in conjunction with the CorPath GRX System. Each device used (e.g., guidewire, microcatheter, coil, etc.) is documented on CRF 9 CorPath GRX Assessment form, and an individual component needs to have successfully navigated to the aneurysm, into the aneurysm, and deployed (if applicable) into the aneurysm to be considered successful.

Subjects to Include: Analysis Cohort

Statistical Analysis: The frequency and proportion of devices successfully used that were used with a CorPath GRX System will be summarized along with a 2-sided Clopper Pearson Exact 95% confidence interval.

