#### CorPath Use Technique

*To obtain proper data for analysis, the following procedure, with associated data collection milestones, is recommended, but in no case, dictates use of the CorPath GRX System in a manner*

*Version Date: May 21, 2021*

*This confidential document is the property of Corindus, Inc. and shall not be reproduced, distributed, disclosed or used without the express written consent of Corindus, Inc.*

*different from that presented in the Operator's Manual.*

**The following CorPath Use Technique guides the Investigator through coiling a cerebral aneurysm with the CorPath GRX System.**

1. Obtain arterial access using conventional technique. Record sheath insertion time.
2. Once arterial access is obtained, insert a standard diagnostic catheter using conventional manual technique or guide catheter mounted coaxially over a diagnostic insert catheter.
3. Manually advance the diagnostic select catheter to the parent vessel.
4. Advance guide catheter to desired location in parent vessel and remove wire and diagnostic select catheter. If only diagnostic catheter was used, then remove standard wire and use exchange length guidewire; remove the diagnostic catheter over the exchange wire while maintaining distal wire position. Advance the guide catheter over the exchange wire to the desired location in parent vessel and remove wire.
5. The Investigator will specify which devices will be delivered robotically.
6. Manually advance microcatheter to tip of guide catheter in the parent vessel.
7. Manually insert exchange length guidewire and attach COPILOT bleed back control valve to the microcatheter.
8. Record microcatheter "insertion" time.
9. Load the microcatheter and exchange length guidewire in the CorPath GRX cassette.
10. Using the CorPath System, advance guidewire and microcatheter independently to target treatment area. The Active Device Fixation (ADF) technIQ automated movement can be enabled to keep the guidewire in place during microcatheter movement.
11. With microcatheter in place, remove guidewire.
12. Advance stent into the COPILOT bleed back control valve and proximal microcatheter slowly and according to stent delivery IFU.
13. Place the stent advancement wire into the Device Track of the CorPath GRX.
14. Advance stent, robotically, to target area. The stent will remain completely sheathed in the microcatheter.
15. Robotically position the stent across target aneurysm.

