16. Maintaining stent position with CorPath GRX, begin to robotically remove the microcatheter with ADF enabled on the microcatheter. This will unsheathe the stent in place.
17. Using micro-millimeter movements with the CorPath GRX, continue to remove micro-catheter until stent is completely unsheathed and fully deployed.
18. Remove stent deployment shaft robotically, reload exchange length guidewire, and re-advance guidewire to target aneurysm.
19. Using robotic manipulation, advance the microcatheter and guidewire wire to position through the stent struts.
20. Robotically retract guidewire.
21. Remove guidewire from cassette and load embolization coils into Device Track.
22. Using the CorPath System, advance embolization coils to target aneurysm. Slowly deploy embolization coils as per physician preference. The Limited Speed technIQ automated movement may be enabled to slow maximum speed to 6mm/sec if

desired. De- tach and exchange embolization coils as per IFU.

23. After embolization of target aneurysm, robotically remove coil delivery catheter and microcatheter.
24. Perform final control angiography.
25. Record final fluoroscopy time, DAP, AK and contrast volume.
26. Record time of microcatheter “removal” time from the parent vessel.
27. Record Operator pocket dosimeter reading.

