#### **4.8.6 Specify Device to Be Used Robotically**

After arterial access prior to using the CorPath GRX System, the Investigator will specify which device he/she will plan to use robotically. If a device that is used robotically cannot be delivered to the target, cross the target or delivered into the target and conversion to manual is needed, it will be documented as an unplanned conversion to manual.

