#### **4.8.7 Conversion to Manual Procedure Data Collection**

The Investigator shall determine if it is necessary to convert to standard manual techniques to complete the endovascular robotic procedure. The Investigator should make this decision based on his/her medical assessment of the situation in accordance with the best interest of the subject. It is recommended that conversion to manual operation be performed at the discretion of the Investigator or if any of the following occur:

- The inability to navigate the guidewire(s), microcatheter(s), embolization coil(s) or stent-assist coiling using the CorPath GRX System as intended.
- Any clinical condition that requires rapid medical intervention. Details of manual technique to be documented are:
  - Planned or unplanned (e.g. physician preference, use of equipment not compatible with CorPath GRX);
  - If unplanned (e.g. embolization coils were undeliverable due to severe tortuosity), specify why.

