### 6.3 Analysis of Secondary Endpoints

Secondary endpoints will be analyzed with descriptive statistics along with a 95% confidence interval. Descriptive statistics for categorical variables will include the number and percentage of subjects in each category, with two-sided 95% confidence intervals of the percentage of subjects in each category. Descriptive statistics of continuous variables will include sample size, mean standard deviation, minimum, median, maximum, and 95% confidence interval of the mean. Summaries will be provided for the overall population and by type of aneurysm (ruptured or unruptured).

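### The Clopper-Pearson interval for pooled device success in SAP 4.4.12 treats devices as independent, so it is too narrow if device failures are positively correlated within subjects

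*SAP*

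**What the plan says.** SAP 4.4.12 (Devices Used Robotically) makes the single device the unit of analysis. To count as a success, "an individual component needs to have successfully navigated to the aneurysm, into the aneurysm" and, where applicable, been deployed there. Successes are pooled over all devices in the Analysis Cohort, and the "proportion of devices successfully used that were used with a CorPath GRX System will be summarized along with a 2-sided Clopper Pearson Exact" 95% interval.

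One subject supplies several devices. The CorPath Use Technique in Protocol 4.8.5 has a guidewire, a microcatheter, possibly a stent, and then coils. Step 9 reads "Load the microcatheter and exchange length guidewire in the CorPath GRX cassette", and step 22 has the operator detach and "exchange embolization coils as per IFU".

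Protocol 6.3 says "Secondary endpoints will be analyzed with descriptive statistics along with a 95% confidence interval" and describes categorical intervals in terms of the percentage of subjects. The device-level unit therefore comes from the SAP. Neither document has a cluster adjustment, a model with a subject effect, or a subject-level version of this endpoint. No hypothesis or performance goal is attached to it.

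**The concern.** Clopper-Pearson gives at least its nominal coverage when the units are independent with a common success probability. Devices used in one subject share the anatomy, the operator and usually the microcatheter. Protocol 4.8.7 itself gives severe tortuosity as a reason why coils could not be delivered, and that cause belongs to the subject rather than to one coil.

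Positive correlation could arise in two ways:

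1. Failure risk differs between subjects, and robotic use continues after a failure.
2. One navigation failure is scored against both guidewire and microcatheter, because each must reach the aneurysm to count as a success.

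In either case the printed 95% interval would overstate how precisely device success is known. Only the description of this secondary endpoint is at stake.

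**Working it through.** **Planning figure.** It is needed here only for the number of subjects and the 90% procedural success rate. SAP 3.2 gives 108 subjects and at least 80% power for 90% against 80%. With one-sided 2.5%, the normal approximation is Φ[(0.10·√108 − 1.96·√(0.8·0.2)) / √(0.9·0.1)] = Φ[(1.039 − 0.784)/0.3] = Φ(0.85) = 80.3%. The exact rule (at least 95 of 108) has 81.0% power. The figure reproduces.

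**Assumptions not in the documents.** 5 devices per subject (540 devices), device success 90%, 95% or 97%, ICC 0.05-0.2, and the share of guidewire and microcatheter failures that are joint.

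**Device success that fits the plan.** If all 5 devices must succeed in 90% of subjects, device success is 0.90^(1/5) = 97.9% under independence. With beta-distributed subject risk it is 97.7%, 97.5% and 97.1% at ICC 0.05, 0.1 and 0.2. The example below uses 524/540 = 97.0%.

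**Coverage of the planned interval.** Simulation with 20,000 replicates and 108 subjects. Coverage is judged against the long-run device proportion under each rule, and ranges are over the three success rates.

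| Robotic use | ICC 0.05 | ICC 0.1 | ICC 0.2 |
|---|---|---|---|
| Ends at first failure | 95-97% | 95-97% | 95-97% |
| Ends at second failure | about 95% | 93-94% | 91-92% |
| Never ends | 93-94% | 90-92% | 86-87% |

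With equal risk, independent failures and no stopping, coverage is 95-96%. At 90% device success, 1 − 0.9⁵ − 5·0.1·0.9⁴ = 8.1% of subjects, about 9 of 108, then have two or more failures. Multiple failures alone therefore do no harm.

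For guidewire and microcatheter failing together, with equal risk in all subjects and stopping at the first failed step, coverage is 95% if 25% of their failures are joint, 93-94% if 50%, and about 91% if all are.

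**Effect on the interval at 524/540.** Design effect = 1 + (5 − 1)·ICC, and effective n = 540 / design effect.

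| | Design effect | Effective n | 95% interval |
|---|---|---|---|
| Planned | 1 | 540 | 95.2-98.3% |
| ICC 0.1 | 1.4 | 386 | 94.8-98.5% |
| ICC 0.2 | 1.8 | 300 | 94.4-98.6% |

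The lower limit moves by 0.4 and 0.8 points, and the upper limit by 0.2 and 0.3 points.

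**The case against.** The strongest objection is that the workflow limits repeat failures. Protocol 4.8.7 recommends conversion to manual when a device cannot be navigated robotically, and 4.8.6 records conversion after a robotic non-delivery. That is closest to ending at the first failure, where the planned interval is sound. This stands as a reason to expect a small effect, but it is not a guarantee. The wording is "It is recommended that conversion to manual operation be performed at the discretion of the Investigator or if any of the following occur", so conversion is left to judgement. In 4.8.6 non-delivery counts only with the further condition "and conversion to manual is needed, it will be documented as an unplanned conversion to manual". Coils are also exchanged one after another.

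The joint-failure route is an inference. Guidewire and microcatheter are loaded together, but step 10 advances them independently, and the documents do not show how CRF 9 would score one failed navigation. A shortfall appears only when the joint share is well above 25%.

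The interval also decides nothing, and robotic performance is reported per subject (SAP 4.2) and per aneurysm (SAP 4.4.2 to 4.4.4) as well. That stands, and it limits the importance of the point.

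A reader might infer that several devices per subject, or several failures in one subject, already invalidate the interval. The simulations do not support that. A reader might also take 90% as the device success rate, which gives larger shifts. With 5 devices and ICC 0.1-0.2, only 65-69% of subjects would then have every device succeed, which does not fit the planned 90% procedural success.

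**Conclusion.** The point holds in conditional form. The planned interval is right if devices fail independently at equal risk, or if robotic use always ends at the first failed device. It is too narrow if failures are positively correlated within subjects, and the documents neither exclude this nor say how often it would happen.

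Under the assumed 5 devices per subject and ICC 0.05-0.2, coverage falls to 86% at worst. That needs robotic use to continue after every failure, at the highest ICC considered. At a device success rate that fits the plan, the limits move by less than 1 percentage point. The point estimate, the sample size, the type I error and both primary conclusions are unaffected. This is a cheap improvement to a descriptive endpoint and does not bear on the trial's conclusions.

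**What to change.** In SAP 4.4.12 keep the device-level point estimate p and state that its 95% interval is computed with subject as the cluster. One workable form is Clopper-Pearson on the effective sample size n / max(1, D). Here n is the number of devices, and D is the between-subject linearised variance of p divided by p(1 − p)/n. If there are no failures, use the planned interval. In the simulations (3, 5 and 8 devices per subject, ICC 0-0.2, joint share 0-100%) this covered 94.8-97.6%. With no clustering it was on average at most about 0.2 points wider in total. Another standard subject-clustered interval, such as a cluster bootstrap or GEE, would also do.

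The cost is one sentence in the SAP and a few lines of code. The only downside is a possibly slightly wider interval.
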